## 6 Hypotheses

In patients with moderate- to severe-OUD between the ages of 18 to 65 years old who seek care or are referred to one of the four RAAM clinics in the North Simcoe Muskoka Local Health Integrated Network for opioid-substitution therapy and are stabilized on Suboxone®, subsequent maintenance therapy with Sublocade® (intervention) versus Suboxone® (control) for a period of 12-months will be superior for reducing opioid positivity (as determined by proportion of negative urine drug screens and self-reports) and healthcare utilization (as determined by the total number of ER visits and hospital days per patient days exposure)

## 7 Objectives

### 7.1 Primary

- 1) To compare the effect of Sublocade® versus Suboxone® on reducing non-prescription opioid utilization in patients with moderate- to severe-OUD
- 2) To compare the effect of Sublocade® versus Suboxone® on reducing healthcare utilization in patients with moderate- to severe-OUD

### 7.2 Secondary

- 1) To compare the effect of Sublocade® versus Suboxone® on improving patient satisfaction
- 2) To compare the effect of Sublocade® versus Suboxone® on improving patient quality of life
- 3) To compare the effect of Sublocade® versus Suboxone® on clinic retention
- 4) To compare the effect of Sublocade® versus Suboxone® on patient mortality

## 8 Design

The **STOP-IT** trial is designed as a pragmatic, multi-centre, randomised, controlled, open-label, superiority study with two parallel groups and primary endpoints of opioid positivity and healthcare utilization at 12 months after enrollment. Randomization will be performed with a 1:1 allocation ratio using a stratified, permuted-block group schema according to the following strata (no fixed ratio):

- 1) RAAM clinic site (Barrie, Orillia, Midland, Wasaga Beach)
- 2) Severity of OUD according to DSM-V criteria (moderate vs severe)

## 9 Study Setting

The four RAAM clinics in the North Simcoe Muskoka Local Health Integrated Network will recruit patients for the study. The North Simcoe Muskoka Local Health Integrated Network is a provincial regional health authority mandated to plan, integrate and fund local health services across the District of Muskoka, Simcoe County and Grey County. This region serves a population of 479 471 (2015), representing 3.5% of the province of Ontario's population. The Network distributes over \$880 million (CDN) in funding to 61 unique health service provider organizations that include 7 hospitals, 21 long-term care homes, 3 community centres, 23 community support services and 7 community health centres. In partnership with the Simcoe Muskoka District Health Unit, the Network developed the Simcoe Muskoka Opioid Strategy in 2017 in response to the higher-than-average provincial rates of opioid-related morbidity and mortality being experienced in the region. Increased access to OAT through the RAAM clinics is an essential component of that strategy (p.38).

The four RAAM clinics are located in the cities of Barrie, Orillia, Midland and Wasaga Beach. These clinics are part of a provincial strategy to remove barriers to access for addiction services and provide a more patient-centred model of addiction services. There are currently 54 RAAM clinics located across Ontario, with the plan to continue to open new RAAM clinics across the province. All the RAAM clinics are based on a similar service model. The four study clinics are owned and managed by the Royal Victoria Regional Health Centre, a 388-bed acute care community hospital in Barrie. Patients can self-refer or be referred for addiction services from any healthcare provider. The clinics provide voluntary outpatient services that include medical and psychosocial treatments for substance use disorders. The clinics are staffed by an interdisciplinary team of physicians, nurse practitioners, registered nurses, registered practical nurses, social workers, addiction counsellors who work together to create a unique treatment plan for each patient. Pharmacotherapy for alcohol and opioid use disorders is available. The clinics do not provide treatment for acute or decompensated mental health illness, treatment for chronic pain disorders or serve as safe injection sites. Since April 1, 2021, there have been 801 consultations, of which 346 involved prescription and non-prescription opioid use.

## 10 Eligibility

Patients must provide written, informed consent before any study procedures occur.

## 10.1 Inclusion criteria

Patients eligible for the trial must comply with all of the following at randomization:

1. Ages 18 to 65 years old
2. OAT indicated for moderate- to severe-[OUD](#)
3. Attend a RAAM clinic in the North Simcoe Muskoka Local Health Integrated Network for opiate substitution treatment
4. Successfully completed induction and stabilization OAT with [Suboxone](#)® tablet or film defined as receiving 8mg/2mg to 24mg/6mg of [Suboxone](#)® for  $\geq 7$  days with no evidence of allergic reaction to [Suboxone](#)®, [Clinical Opiate Withdrawal Scale](#) (COWS) score  $\leq 12$  (scale:0-48) for  $\geq 24$  hours, and [Opiate Craving Visual Analog Scale](#) (VAS) score  $\leq 20$  (scale:0-100) for  $\geq 24$  hours
5. Must have an active Ontario Health Insurance Plan number
6. Must have a telephone that can receive calls, text messages or emails
7. Must have drug insurance coverage for either medication for duration of study or demonstrate ability to pay for the drug out-of-pocket

## 10.2 Exclusion criteria

1. Receiving any investigational drug for [OUD](#) in previous 4 weeks
2. Congenital long  $QT_c$  syndrome or  $QT_c$  prolongation at baseline by electrocardiogram ( $QT_c \geq 450$  milliseconds in men and  $QT_c \geq 470$  milliseconds in women)
3. Pregnant or lactating women
4. Women of childbearing potential who are not using an effective and reliable method of contraception

# 11 Interventions

## 11.1 Medications

Eligible patients will be randomly allocated in a 1:1 ratio between [Suboxone](#)® and [Sublocade](#)®. Both study drugs will be provided to participants in their commercially available forms. For those patients who are not eligible for drug coverage under the Ontario Drug Benefit Plan or other insurance plan, eligible patients must demonstrate the ability to pay for either medication out-of-pocket. The commercially available drugs will be provided by the RAAM clinics ([Sublocade](#)®) or pharmacies ([Suboxone](#)®) as per the usual process of care. This is an open-label study so no changes in labelling or packaging will take place, and both drugs will be stored, handled, administered and disposed of in accordance with the manufacturer's recommendations and the RAAM clinics' and pharmacies' standard operating procedures (SOPs). This is a pragmatic, comparative effectiveness study so the management of the participants and their medications in the RAAM clinics will be left up to the discretion of the RAAM healthcare personnel who have all received training and are experienced in the diagnosis, management and treatment of [OUD](#).

For eligible patients randomly allocated to Sublocade®, the first dose will be administered at the time of randomization (Day 0). Sublocade® comes in two formulations, 100 mg and 300 mg buprenorphine doses in a pre-filled syringe. Sublocade® administration is by subcutaneous injection in the abdomen. Sublocade® is administered at intervals  $\geq 26$  days. For patients randomly allocated to Sublocade®, they will receive the 300 mg dose for the first 2 months, followed by the 100 mg dose every month until the end of the 12-month period. All Sublocade® doses will be administered in the RAAM clinics by trained personnel according to SOPs. All patients receiving Sublocade® will have their vital signs monitored every 5 minutes for 15 minutes after the injection before leaving the clinic.

For eligible patients randomly allocated to Suboxone®, the first study dose will be administered at the time of randomization (Day 0) and will match the Suboxone® type (tablet versus film), route (sublingual versus buccal) and dose used for stabilization prior to study enrollment. For the first 2 weeks of the study period, all Suboxone® administration will be directly observed at community pharmacies by trained personnel according to the usual standard of care. Subsequent to this period, healthcare providers and participants will develop a care plan for ongoing directly observed therapy vs unsupervised take-home dosing according to usual standard of care.

## 11.2 Counselling

For eligible patients enrolled in the study, each will receive individual patient counselling for addictions, mental health and trauma by trained RAAM clinic personnel at each clinic visit according to the usual standard of care. In addition, each participant will be provided with links to community social support services. For those participants who need it, connection to a primary care provider will be provided.

## 11.3 Screening

For eligible patients enrolled in the study, each will receive pregnancy screening at regular intervals. Female patients of child-bearing age will also be questioned about contraceptive use, and counselled about the potential risks of OUD treatment in pregnancy. Screening for illicit drug use will be done using a combination of a validated self-reporting tool and urine drug testing at each clinic visit. Screening for opioid withdrawal and craving will be done at each clinic visit. Weight, vital signs and mental status will be screened at each clinic visit.

## 11.4 Modifications

For eligible patients randomly allocated to Sublocade®, missed doses can be administered up to 42 days after the last dose. For those with longer intervals between Sublocade® doses, it will be up to the discretion of the RAAM clinic healthcare providers whether repeated induction and stabilization with Suboxone® is required, and if Sublocade® treatment should be re-

initiated. At the discretion of the RAAM clinic healthcare providers, some participants may receive breakthrough doses of Suboxone® and/or an increased maintenance dose of Sublocade® of 300 mg per month instead of 100 mg per month as clinically indicated to prevent opioid cravings (VAS  $\geq$  21) or withdrawal (COWS  $\geq$  5) symptoms. In some cases, Sublocade® doses may need to be reduced or discontinued due to adverse effects.

For eligible patients randomly allocated to Suboxone®, at the discretion of the RAAM clinic healthcare providers, some participants may receive breakthrough doses of Suboxone® and/or increased maintenance doses of Suboxone® as clinically indicated to prevent opioid cravings (VAS  $\geq$  21) or withdrawal (COWS  $\geq$  5) symptoms. Daily dose of Suboxone® should not exceed 24 mg buprenorphine. In some cases, Suboxone® doses may need to be reduced or discontinued due to adverse effects.

For eligible patients with abnormal vital signs (a change from baseline measurements and any of the following: systolic blood pressure  $\leq$  90 mm Hg OR mean arterial blood pressure  $\leq$  55 mm Hg OR heart rate  $\geq$  130 beats per minute OR temperature  $\geq$  38.1°C OR  $\leq$  36°C OR respiratory rate  $\leq$  8 breaths per minute OR  $\geq$  30 breaths per minute or mental status (Glasgow coma scale  $\leq$ 14), RAAM healthcare personnel will investigate the causes for these abnormalities prior to consideration of buprenorphine dosing, and make all necessary arrangements for medical management of the patient.

For eligible patients who have either a positive urine drug screen, illicit drug use by self-report, or refuse to submit to these screens, individualized patient counselling with an addictions counsellor will attempt to understand the underlying reasons for relapse or refusal to screen as per usual standard of care. RAAM healthcare personnel will take into consideration opioid positivity (either positive urine drug screen or self-report) or refusal to screen prior to the administration of study medications.

For eligible patients with a positive pregnancy test after a negative pre-enrollment test, RAAM healthcare personnel will counsel the patient about the potential negative effects (teratogenicity, neonatal opioid withdrawal syndrome) of ongoing study medication treatment, and the options for alternative management of OUD as per usual standard of care.

### 11.5 Retention and adherence

For eligible patients enrolled in the study, retention and adherence interventions will include:

- 1) Phone call 2 days before each scheduled clinic visit to determine if there will be any barriers to attending the scheduled visit, and working on solutions to remove these barriers to maximize compliance with scheduled visits
- 2) Assistance to complete scheduled questionnaires (quality of life and medication satisfaction) either in clinic or remotely
- 3) Provide in-home laboratory and electrocardiographic services as needed if a patient cannot travel to the lab site

- 4) Instructions about taking study tablets/films including dose timing, route, storage, and what to do in the event of a missed dose
- 5) All participants will be provided with the RAAM clinic's nurse practitioner's contact number with instructions to call if experiencing problems possibly related to study treatment such as symptoms or lost pills.

## 12 Outcomes

### 12.1 Primary outcome measures

#### 12.11 Opioid positivity

Difference in proportions of relapse-free weeks (RFWs) at 12-months from the date of randomization, where ***relapse-free weeks are defined by the cumulative number of weeks alive during the study period in which there was a negative urine drug screen and negative self-report for non-prescribed opioids.*** The potential number of RFWs for each patient is the cumulative number of weeks that the patient is alive during the 12-month study period, with a maximum of 48 weeks. A week is defined as a consecutive 7-day period starting on the day of the week that randomization occurred. A patient is considered to have 'completed' a week as long as they are alive for  $\geq 1$  day of that week. For example, if a patient is randomized on a Tuesday, and subsequently dies on a Thursday of the 32nd week, the patient will have been considered to have been alive for 32 weeks. The denominator used in estimating the proportion of RFWs will be the total number of weeks that the patient was alive during the study period. Vital statistics for all participants (date and year of death) will be available through linkage with the Office of the Registrar General of Ontario database. The cumulative number of RFWs alive will be used as the numerator in estimating the proportion of RFWs. Scheduled urine drug testing and self-reports will occur every 2 weeks during the study period starting in week 2 from randomization. Imputation of missing data will occur for those weeks in which a urine drug screen/self-report was not scheduled according to the results of the subsequent week's urine drug screen/self-report. For example, if a urine drug screen/self-report was not scheduled for week 11, but a scheduled urine drug screen/self-report was done on week 12 and week 12 met the criteria for a RFW, then week 11 would be imputed as a RFW (Figure 1). Similarly, for weeks with scheduled urine drug screen/self-reports that are missed, that week and the preceding week in which there was no scheduled urine drug screen/self-report will not be counted as RFWs (for example, see Figure 1, week 17 and 18). In the hypothetical patient represented in Figure 1, 20 urine drug screens/self-reports were completed, with 5 positive and 15 negative urine drug screens/self-reports, resulting in 30 cumulative RFWs over the 48-week study period, or a proportion of RFWs of 0.625.

**Figure 1: Schematic for a hypothetical participant and measurement of RFWs**

Variable	Weeks																								
	0	2	4	6	8	10	12	14	16	18	20	22	24	26	28	30	32	34	36	38	40	42	44	46	48
UDS/Self-report 		-	+	-	-	+	-	-	+	na	-	-	+	-	na	-	-	+	-	na	-	na	-	-	-
RFWs		2	2	4	6	6	8	10	10	10	12	14	14	16	16	18	20	20	22	22	24	24	26	28	30

 - = negative urine drug screen (uds) and self-report , + = positive urine drug screen and/or self-report, na=not available/missing

### 12.11a Urine drug testing

The RAAM clinics perform on-site presumptive urine drug testing using Health Canada-approved, lateral flow immunoassay-based point-of-care tests (Rapid Response™ Multi Drug Test Panel, BNTX Inc., Product code: D-1P-07). This qualitative urine assay uses established cut-off values for addictive substances or their metabolites to identify their presence (positive) or absence (negative). The urine assay can detect the following addictive substances/metabolites: benzodiazepines, buprenorphine, cocaine, ethyl glucuronide, fentanyl, morphine, oxycodone, EDDP, hydromorphone, and methamphetamine. In addition, the assay also measures urine pH and urine creatinine to screen for specimen integrity. All results are available in 5 minutes. All RAAM clinic healthcare providers must receive training and certification before use of this assay, and biennial re-certification is required. Internal and procedural controls are included in the assay to indicate proper volume of specimen added and that wicking has occurred. In addition, the Royal Victoria Regional Health Centre Laboratory Services is responsible for quality control checks with each new lot number prior to release to the RAAM clinics for use. Definitive urine drug testing will not be used to validate the results of any urine drug test, but at the discretion of the RAAM clinic healthcare providers, may be used to investigate discrepancies between presumptive urine drug test results and self-reports, or detect unexpected addictive substances not available through presumptive testing. While urine sample collection is not directly observed by RAAM clinic healthcare providers, all urine samples must be collected during the clinic visit. To reduce the risk of urine tampering, each urine sample is inspected for temperature, colour, smell and appearance in addition to measuring urine pH and urine creatinine. Any urine sample that is considered substituted or invalid is discarded, and the patient will be imputed to have a positive urine drug test for that scheduled clinic visit. Urine drug screens and self-reports will only occur on day of the scheduled clinic visit, and there will be no opportunity to provide a urine sample either before or after the scheduled clinic visit.

### 12.11b Opioid use self-reports

Opioid use self-reporting will accompany each scheduled urine drug test. Opioid use self-reporting will be measured using the Timeline Followback questionnaire. This questionnaire will be administered by RAAM clinic healthcare personnel. The questionnaire consists of asking patients to recall and document their use of any addictive substances in the questionnaire on

any or all of the 7 days preceding the clinic visit. A positive self-report will be defined as any report of the use of non-prescribed opioids in the preceding 7 days.

#### 12.12 Healthcare utilization

Difference in incidence rates of healthcare days at 12-months from the date of randomization, where **healthcare days represent the number of days alive and registered for an emergency room visit or admitted to an acute care or mental health facility for opioid-related harms or poisonings**. For each group, the incidence rate is calculated by dividing the total number of healthcare days by the total person days exposure over the study period. The potential number of healthcare days for each patient is the number of days alive during the 12-month study period, with the maximum being 365 days. Any day in which a patient is documented to have had an emergency room visit or is admitted to an acute care or mental health facility for any opioid-related harm or poisoning will be counted as a healthcare day. To estimate the number of opioid-related harms and poisonings resulting in healthcare utilization, the Discharge Abstract Database, Ontario Mental Health Reporting System database, National Ambulatory Care Reporting database, Registered Persons Database, and Office of the Registrar General of Ontario database will be linked to each patient's Ontario Health Insurance Plan number and the following opioid-related harms and poisonings International Statistical Classification of Diseases and Related Health Problems, Tenth Revision, Canada (ICD-10-CA) codes will be used to estimate the number of healthcare days utilized during the study period: Y45, F11.0-F11.9, T40.0-T40.4, T40.6. All opioid-related harms and poisonings resulting in the utilization of a healthcare day regardless of intent (ICD-10-CA X42 (accidental), ICD-10-CA X62 (intentional), and ICD-10-CA Y12 (undetermined)) will be included in the final analysis. Only those healthcare days in which opioid use was considered to be influential to the ER visit or hospitalization will be included and are identified by the following ICD-10-CA codes: M (most responsible diagnosis), 1 (pre-admit comorbidity), 2 (post-admit comorbidity), W or X or Y (Service transfer diagnosis). In addition, Diagnostic and Statistical Manual of Mental Disorders, 5th Edition codes 304.00 and 305.50 will be used to capture healthcare days for opioid-related harms and poisonings.

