#### 18.11 Routinely collected data

##### *18.11a Prior to induction*

For all RAAM clinic patients with OUD who are eligible to receive any opiate substitution therapy, the following demographic and baseline clinical and laboratory data are collected **prior to induction** with any treatment (Table):

Data	Description	Data type
Demographics		
Date of birth	Month/day/year	Mm/dd/yyyy
Sex at birth	Male: Female	Categorical
Pregnant	Yes: No	Categorical
Ontario health insurance plan number	Unique provincial insurance number assigned to every resident	xxxx-xxx-xxx-version code
Ontario drug plan status	Insured versus non-insured	Categorical
Residency	Homeless; transient (< 6 months at same address, couch surfing or shelter); stable (≥ 6 months at same address)	Categorical
Children in home	Yes: No	Categorical
Children ages	Years	Continuous
Telephone contact	Yes: No	Categorical
Number		(xxx)-xxx-xxxx
Employment status 	Full-time (≥ 40 hours per week for ≥ 90 days per year); Part-time (≤ 40 hours per week or ≥ 90 days per year); Casual (≤ 90 days per year); unemployed	Categorical
Incarceration 	Incarceration in ≤ 12 months (Yes: No)	Categorical
Race 	White: Non-white, non-indigenous: Indigenous	Categorical
Clinical		
OUD diagnostic screen	≥ 2 of 11 DSM-V criteria must be present ≤ 12 months for diagnosis of OUD	Categorical: range 0 to 11:
OUD severity	DSM-V criteria of mild, moderate or severe OUD	Categorical: mild (2-3 criteria); moderate (4-5 criteria); severe (≥6 criteria)
Medical history	Comorbid illness screen, including mental health and substance use	Categorical
Medications	Prescribed	Categorical

Alcohol use	Yes: No	Categorical
Opioid use	Type: Route	Categorical
Other substance use	Type: Route	
Recent substance/opioid use	Timeline Followback questionnaire (assesses use and frequency of use of substances over the previous 7 days)	Categorical
Hospitalization	Substance-related $\leq$ 12 months (includes emergency room visit, admission to hospital, mental health or detoxification facility) (Yes: No)	Categorical
General physical exam	Vital signs; height; weight	Continuous
Opioid withdrawal screen	$\geq$ 3 of the following: dysphoria; nausea or vomiting; muscle aches; lacrimation or rhinorrhea; pupillary dilation or piloerection or sweating; diarrhea; fever; insomnia; yawning	Categorical; range 0-9
Jaundice	Yes: No	Categorical
Mental status	Glasgow coma scale	Categorical (range 3-15)

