### 20.11b Healthcare utilization

We will model the days of healthcare utilization as count data, with the period of follow-up while alive during the study period as the exposure period. We will analyse the data using a Poisson regression model. We will include an indicator for OUD severity. We will include any baseline demographic or clinical variables that are unbalanced at Level 1.

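### Exposure for the healthcare-utilization co-primary ends early only at death, so days after a participant's Ontario coverage or residence ends would probably count as event-free

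*Combined protocol and SAP*

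**What the plan says.** **Exposure.** Section 12.12 defines the rate by arm: "the incidence rate is calculated by dividing the total number of healthcare days by the total person days exposure over the study period". It then adds: "The potential number of healthcare days for each patient is the number of days alive during the 12-month study period", with a ceiling of 365. Section 20.11b models healthcare days as a count, "with the period of follow-up while alive during the study period as the exposure period", and states "We will analyse the data using a Poisson regression model". Section 18.22 keeps participants who withdraw, or are withdrawn, under observation to the end of the study period for outcomes taken from routine data, and names healthcare utilization as an example. It also says that loss to follow-up is not a withdrawal.

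**Events.** Section 12.12 lists five databases that "will be linked to each patient's Ontario Health Insurance Plan number". Section 18.13 says that the utilization data come through the Institute for Clinical Evaluative Sciences, and describes its remit as evaluating and monitoring Ontario's health system. Deaths come from the Ontario registrar's database (Sections 12.11 and 12.12).

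**Coverage.** Section 10.1 opens with "Patients eligible for the trial must comply with all of the following at randomization" and lists as item 5 "Must have an active Ontario Health Insurance Plan number". No section requires coverage to continue, checks it later, or ends exposure when it stops.

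**The concern.** A rate is interpretable only if numerator and denominator cover the same person-time. Here the denominator runs to death or day 365, while the numerator depends on a provincial health number that has to be active only on the day of randomization. Once coverage or residence ends, the participant would probably go on adding days on which the linkage cannot record an event, and each such day is scored as a day without healthcare use. A death outside Ontario might be missed too, which would leave that person counted as alive.

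At stake is a co-primary outcome that Section 12.12 words as a difference in incidence rates. Exits that are equal in both arms pull that difference towards zero. Unequal exits also bias the rate ratio, in favour of the arm that more people leave. Equality cannot be taken for granted: the trial is open-label, and one arm has clinic injections while the other has pharmacy dispensing.

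**Working it through.** **Step 1. When does exposure end?**
- Section 12.12: potential days are days alive, at most 365.
- Section 20.11b: follow-up while alive.
- Section 18.22: for this outcome, follow-up continues for the whole study period even after withdrawal.
- Section 14.3, Table 4, footnote 2: exposure is halved for 50% loss to follow-up.

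The first three together leave death as the only early stop. The fourth assumes a loss of exposure that the other three do not recognise.

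**Step 2. The plan's own exposure figure.** 20 × 365 × 0.5 = 3650 patient-days per group, which reproduces. For the planned 45 per arm, the days-alive rule gives 45 × 365 = 16,425 days, and the Table 4 discount would give 16,425 × 0.5 = 8,212.5. The two readings differ by a factor of two. (The 99% power attached to 3650 days does not reproduce: 7.3 against 3.65 expected events give about 20%. That is a separate matter, and nothing here rests on it.)

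**Step 3. Effect on one arm's rate.** The documents give no exit rate, so the exits are assumed. Other assumptions: leavers have the same event rate as the rest, no event is captured after exit, and there are no deaths. With U unobservable days, observed rate = true rate × (1 − U/16,425).

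| Assumed exits of 45 | U | Share of exposure | 2.0 per 1000 days becomes |
|---|---|---|---|
| 1 on day 30 | 335 | 2.0% | 1.96 |
| 3 on day 30 | 3 × 335 = 1,005 | 6.1% | 1.88 |
| 5 at mid-year | 5 × 183 = 915 | 5.6% | 1.89 |

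**Step 4. Effect on the comparison.** Take the plan's rates of 2 (Suboxone) and 1 (Sublocade) per 1000 days. If a fraction f leaves, on average at mid-year, observed rate = true rate × (1 − f/2).

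| Exits | Observed rates | Ratio | Difference |
|---|---|---|---|
| None | 2.00 / 1.00 | 0.50 | 1.00 |
| 5% in both arms | 1.95 / 0.975 | 0.50 | 0.975 |
| 10% in both arms | 1.90 / 0.95 | 0.50 | 0.95 |
| 20% in both arms | 1.80 / 0.90 | 0.50 | 0.90 |
| 10%, Suboxone only | 1.90 / 1.00 | 0.526 | 0.90 |
| 10%, Sublocade only | 2.00 / 0.95 | 0.475 | 1.05 |

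As an outer case, suppose there is no true effect (2 against 2) and 20% (9 of 45) leave one arm only. The ratio is then 1.8/2.0 = 0.90 if they leave Sublocade, or 2.0/1.8 = 1.11 if they leave Suboxone.

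**Step 5. Size against sampling error.** Expected events over 16,425 days are 32.85 and 16.425. The Poisson standard error of the log rate ratio is √(1/32.85 + 1/16.425) = 0.302. Three day-30 exits in one arm shift the log ratio by |ln(1 − 0.0612)| = 0.063, and 0.063/0.302 = 0.21 standard errors. One such exit gives 0.0206/0.302 = 0.07. Overdispersion would widen the standard error and make these fractions smaller.

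**The case against.** **The plan may already allow censoring.** The days-alive sentence in Section 12.12 caps the count and does not expressly define the denominator. Section 20.11b ties exposure to follow-up, and Section 14.3 discounts exposure for loss. The wording is indeed open. But Section 18.22 makes follow-up for this outcome run to the end of the study period, the Section 14.3 discount is a power assumption, and no rule says when linked follow-up stops.

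**Ontario-only capture is not stated.** This stands. Two of the five databases are Ontario sources by name; the reach of the others is not given. The inference rests on the linkage key and the data holder. The data holder's letter (Section 34.6) also refers to a research plan that is not in the text available here and might fix an observation window.

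**The effect is small and the remedy imperfect.** Both stand. Against a target reduction of at least 50% (Section 14.1), a shift of 2% to 6% is minor. Censoring at exit is unbiased only if leaving is unrelated to risk.

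**Stronger readings that the documents do not support.** A reader might infer from the residency categories in Section 18.11a ("Homeless; transient (< 6 months at same address, couch surfing or shelter") that many participants will leave the province. Those categories describe stability of address, not moves out of Ontario. A reader might also infer that a leaver is scored near-worst on relapse-free weeks and best possible on healthcare days. A day-30 leaver can reach at most 4/48 = 0.083 on the former, but a mid-year leaver can reach about 0.5. Healthcare days before exit are still counted, so the utilization score need not be zero.

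**Conclusion.** The gap is real but minor. As written, exposure for this co-primary is the full time alive up to 365 days, while event capture depends on a linkage that probably stops working when Ontario coverage or residence ends. The affected arm's rate is then too low. Under equal exits the rate difference shrinks and the ratio does not move; the ratio is biased only if exits differ by arm.

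Under the assumed exits (one or three of 45 on day 30, or five at mid-year, in one arm only), the rate shifts by about 2% to 6%, at most about 0.2 standard errors. The shift would be larger if leavers are heavier users of care. The conclusion rests on the inferred Ontario-only capture and on exit numbers that the documents do not supply. It does not support a claim that the co-primary result will be materially wrong.

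**What to change.** In Sections 12.12 and 20.11b:
- Define exposure as the time from randomization to the earliest of death, day 365, or the end of Ontario coverage or residence shown in the Registered Persons Database. That database is already on the linkage list; confirm with the data holder that it has such dates.
- Count events over the same interval.
- Report the number and timing of exits by arm.
- Keep the days-alive denominator as a sensitivity analysis, because censoring removes the bias only if leaving is unrelated to risk.
- Reconcile the rule with the 50% discount in Section 14.3 and the continued follow-up in Section 18.22.

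The cost is a short addition to each section, one extra date variable in the data request, and slightly less exposure. If 5%, 10% or 20% of an arm left on average at mid-year, 16,425 × (1 − f/2) gives about 16,014, 15,604 or 14,783 days instead of 16,425. The rule is best fixed before the linked data are seen, since Section 17 leaves the analysts unmasked.
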